11.5 Treatment Failure

It should be noted that ipsilateral breast tumor recurrences (IBTR) do not cause a diminished overall survival. Nonetheless, they do represent a failure of breast conservation. We will assess the

possibility of an unexpected rise in IBTR by comparing the observed IBTR rate to that expected from an exponential distribution with an event rate of 5% over 5 years. The assessment is repeated every 6 months during the patient accrual phase of the study and once a year thereafter to the end of the five-year follow-up period. A Hochberg stepdown procedure, implemented by SAS proc multtest, will be used to adjust the p-values for multiple looks.

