11.0 STATISTICAL CONSIDERATIONS

11.1 Specific Aims

11.1.1 Specific Aim 1

We will quantify the tolerance of HG-PBI by estimating the rate of acute and late treatment-related grade 3 or higher toxicity (per CTCAE, v.4.0) or any other grade 4 or 5 toxicity attributed to the therapy. Toxicities of concern include breast pain, delayed wound healing, persistent seroma fluid accumulation, breast fibrosis and fat necrosis in the treated breast.

Rare toxicities include radiation pneumonitis and pericarditis. *Hypothesis:* Morbidity occurs in approximately 5-8% of patients with a maximum allowable proportion with grade 3-5 toxicities of 12%. A sequential probability ratio stopping rule will be used to monitor the toxicity rate during the trial.

11.1.2 Specific Aim 2

We will estimate the ipsilateral breast tumor recurrence rate at 5 years after HG-PBI as the sole radiation therapy technique following partial mastectomy. *Hypothesis:* The IBTR will be less than 15.9% with 95% confidence resulting in a treatment strategy worthy of further investigation in a larger clinical trial.

11.1.3 Specific Aim 3

We will estimate the change in breast cosmesis over time using the validated, quantitative parameter pBRA. *Hypothesis:* The pBRA will not significantly change over time. We have previously demonstrated this in the setting of multicatheter APBI.[20]

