11.3 Study Design and Analysis Plan

This is a single arm, non-randomized phase I/II study of 50 patients with stage 0 (tumor size $\leq 2\text{cm}$) or I breast cancer. The primary study goal is to quantify the tolerance of HG-PBI by estimating the rate of acute and late treatment-related grade 3 or higher toxicity (per CTCAE, v.4.0) or any other grade 4 or 5 toxicity attributed to the therapy. Toxicities of concern include breast pain, delayed wound healing, persistent seroma fluid accumulation, breast fibrosis and fat necrosis in the treated breast. Rare toxicities include radiation pneumonitis and pericarditis. These are expected to occur in approximately 5-8% of patients with a maximum allowable proportion with grade 3-5 toxicities of 12%. A sequential probability ratio stopping rule will be used to monitor the toxicity rate during the trial. For example, the study will be suspended for review of toxicity if 4 cases of grade 3-5 toxicity are seen among the first 14 patients, or 5 among the first 26 patients. The full criteria for monitoring are given in the table below. All toxicities and other serious adverse events will be reported to the Clinical Trials Office and to QASM as described.

The study will be suspended for review if:	
this number of patients are	before this number of patients

observed with grade 3-5 toxicity:	have completed the trial:
4	14
5	26
6	38
7	50

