11.4 Sample Size and Study Power

Although the primary goals of this study include tolerance to treatment, the sample size for this study is based on the proportion of patients who remain free from an ipsilateral breast cancer recurrence (IBTR) 5 years after treatment which will be compared with the current expected value in the medical literature. Fyles reported that the five-year IBTR in a large population of women ≥ 50 yr with pT1N0 estrogen receptor positive breast cancers treated with partial mastectomy and tamoxifen but no radiation therapy was 5.9%[39]. HG-PBI will be considered worthy of further investigation if 1) the treatment-related toxicity rate as described above is less than 12% and 2) the five-year IBTR is not significantly greater than 10% higher than that observed in the Fyles study. Binomial proportion power analysis, assuming an alpha-level of 0.05, determined that we will obtain approximately 70% power to detect a proportion significantly larger than 15.9% given the true five-year IBTR is the same as that observed in the Fyles study. If 50 patients complete the trial and more than 3 recurrences are observed in the first five years, then the observed rate will be significantly larger than the acceptable proportion. Consequently, if 3 or fewer recurrences are observed among 50 patients and the tolerance parameters are met, the study will conclude that there is preliminary evidence that HG-PBI as performed in this trial is worthy of further study.

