11.6 Accrual

It is estimated that less than 10% of the patients treated in this study will be lost to follow up. Therefore, because the accrual goal is 50 evaluable patients (at 5 years post-treatment), target accrual is 55 patients to account for the 10% anticipated drop-out. It is estimated that patient accrual will take two to three years.

The investigators are well aware that several prior clinical trials that involved breast cancer at the Washington University Medical Center and the Siteman Cancer Center suffered from poor accrual. We believe that this trial will have excellent patient accrual. The primary source of patients who may be eligible for this study is via the breast surgeons of the Section of Endocrine and Oncologic Surgery here at Washington University. The chief breast surgeon is a collaborator in this study and is very supportive. The fact that a large fraction of patients with a common cancer disease are eligible for this study should lend further reassurance that this study ought to enjoy excellent patient accrual. The following series of conservative estimates provide an approximation of patient accrual: in 2012 more than four hundred patients with breast cancer were seen by physicians in the Department of Radiation Oncology. A conservative estimate is that 20% of these patients had an early stage breast cancer that would be eligible for this study. A further conservative estimate is that a third of these patients will consent to participate in this study. This yields an estimated accrual of just over 25 patients per year.

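### Section 11.5 adjusts sequential IBTR looks by Hochberg, which needs the complete set of p-values, so no flag threshold is fixed when a look is made; a pre-set person-year boundary should replace it

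*Combined protocol and SAP*

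**What the plan says.** Section 11.5 sets up interim surveillance for an unexpected rise in IBTR. The observed rate is set against that "expected from an exponential distribution with an event rate of 5% over 5 years". On timing: "The assessment is repeated every 6 months during the patient accrual phase of the study and once a year thereafter". The yearly looks continue until follow-up closes at five years. On multiplicity: "A Hochberg stepdown procedure, implemented by SAS proc multtest, will be used to adjust the p-values for multiple looks".

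The section gives no test statistic, significance level, sidedness, number of looks, cut-off or consequence of a positive look. It does not say whether the adjusted family is the looks so far, all planned looks, or the completed set.

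Two other parts of the plan bear on this:

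- **Toxicity (Section 11.3)** has a count table fixed in advance: "The full criteria for monitoring are given in the table below".
- **The final IBTR decision (Section 11.4)** is a separate rule. The treatment is judged worthy of further study "if 3 or fewer recurrences are observed among 50 patients and the tolerance parameters are met". Section 11.1.2 gives the matching hypothesis: "The IBTR will be less than 15.9% with 95% confidence".

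**The concern.** Hochberg's adjustment orders a finished set of p-values, and each adjusted value depends on the others in the set. Applied to looks that accumulate over seven or eight years, it leaves two workable readings:

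- **(A) Looks to date.** The adjustment is re-run at each look. The threshold moves as looks are added, so a flag raised at one look can disappear at the next.
- **(B) All looks as one family**, or one adjustment at the end. This behaves almost like a level of 0.05/K at every look, where K depends on how long accrual takes and is unknown until accrual ends.

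The label adds doubt, since Hochberg is a step-up method and the text calls it stepdown. Two statisticians with the same data could disagree on whether a flag had been raised. At stake is the only statistical interim check on an endpoint that is a primary objective and drives the sample size.

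**Working it through.** **Inputs from the documents.** Reference 5% over 5 years, exponential (11.5). Looks every 6 months in accrual, then yearly (11.5). On accrual, "It is estimated that patient accrual will take two to three years" (11.6). 55 enrolled (11.6); 5-year follow-up (11.3). The 15.9% rate of concern comes from 11.1.2 and 11.4.

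**Assumptions not in 11.5.** One-sided exact Poisson test at 0.05; uniform entry over 2, 2.5 or 3 years; no drop-out in the main runs. Section 11.5 states no operating figure, so there is none to reproduce.

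**1. Reference hazard and number of looks.** λ0 = −ln(0.95)/5 = 0.01026 per year. K = 4+5 = 9, 5+5 = 10 or 6+5 = 11 for the three accrual lengths.

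**2. A flag that disappears under (A), 2-year accrual.**

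- Month 6: 13.75 patients × 0.25 years = 3.44 person-years, so 0.0353 events expected. One IBTR gives p = 1 − exp(−0.0353) = 0.0346, a flag.
- Month 12, no further event: 27.5 × 0.5 = 13.75 person-years, 0.141 expected, p = 1 − exp(−0.141) = 0.132.
- The Hochberg-adjusted first p-value is min(2 × 0.0346, 0.132) = 0.069. The flag is gone.

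**3. Reading (B).** 0.05/K = 0.0056, 0.0050 or 0.0045. A constant level tuned to B's false-alarm rate comes out at 0.0056/0.0050/0.0046, so B is in effect that rule.

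**4. An example pre-set rule.** Flag if at least 2 IBTRs have occurred and P(X ≥ k | λ0 × person-years) ≤ 0.02. Solving for person-years gives 20.9, 55.3, 99.1, 149.1, 203.6 and 261.6 for k = 2 to 7. Total follow-up cannot exceed 55 × 5 = 275 person-years, so k = 8 covers the remainder.

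**5. Simulated performance (2 / 2.5 / 3-year accrual).**

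| Method | False alarms, true 5% | Detection, true 15.9% | Detection during accrual | False alarms during accrual |
|---|---|---|---|---|
| (A) looks to date | 5.1/4.6/4.0% | 72/70/68% | 24/30/30% | 4.2/4.0/3.6% |
| (B) all looks | 1.4/1.1/1.1% | 67/65/64% | 15/17/20% | not tabulated |
| Example rule | 3.9/3.8/4.6% | 81/81/82% | 26/28/37% | 2.0/1.9/2.6% |
| One unadjusted final test | 2.2% | 80% | none | none |

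Rounding the person-year limits down gives 3.8/3.7/4.6% false alarms and the same detection. Under (A), look 1 alone accounts for more than half the false alarms (3.3/2.9/2.2% of trials). Of null trials ever flagged, 72–77% are no longer flagged at the last look (Monte Carlo error about 1 point).

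**6. At equal false alarms.** A constant level (minimum 2 IBTRs) tuned to A's rate for each accrual length detects 84/83/80%, a gain of 12/13/11 points. Tuned to B's rate it detects 67/65/64%, a gain of zero. With a mid-p test the gain over (A) is 6–10 points; with an O'Brien-Fleming-shaped boundary and the exact test it is 15–19.

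**7. Where the gain falls.** Flags raised at a true 15.9% rate with 3 or fewer IBTRs seen: (A) 19/21/19%, example rule 20/19/21%, a difference of +1/−2/+2 points. During accrual the difference is +2/−2/+7 points from the rounded table entries.

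**8. Sensitivity.** With 10% drop-out: (A) 70/69/66%, (B) 66/63/63%, example rule 79/78/79% at 4.1/3.6/4.2% false alarms. With a normal-approximation test, (A) detects 86–88% but at 15–17% false alarms. At a true 10% rate all are weak: (A) 24–28%, (B) 18–21%, example rule 35–37%.

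**9. The final rule.** P(X ≥ 4 | 50, 0.159) = 0.968, so Section 11.4 still fails a treatment with a true 15.9% rate in 96.8% of trials. P(X ≥ 4 | 50, 0.05) = 0.24, so four IBTRs could not itself serve as a 5%-level flag against the 11.5 reference.

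**The case against.** The case for leaving 11.5 alone is that it only says p-values will be adjusted. It sets no stopping rule, so detection power for a flag without a stated consequence is partly a construct. Treatment is a single fraction, so after accrual no flag can change exposure. Several stronger readings are also tempting and do not hold:

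- **That Hochberg costs this trial 11–13 points of detection.** That figure needs reading (A), a one-sided exact Poisson test at 0.05 and a constant level tuned to each accrual length. None of these is in 11.5. Other choices that the text allows give anything from zero to 19 points.
- **That the pre-set rule gives much earlier warning.** It does not: against (A) it is slightly worse during accrual at 2.5 years, and nearly equal before the fourth IBTR.
- **That IBTR is otherwise unwatched.** Section 10.0 requires the investigator to review all patient data at least every six months and to report efficacy measures to the monitoring committee. A rising count would be seen, though without a statistical boundary.
- **That the trial's conclusion is compromised.** The rule in 11.4 stands apart from 11.5.

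These points limit the size of the concern. They do not supply a threshold. Section 10.0 also asks the report to list early stopping rules with supporting data, and 11.5 offers no fixed IBTR rule to list. The 0.02 level and the two-event minimum are one choice among several sound ones.

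**Conclusion.** The concern holds as a defect of interim monitoring. The named method does not fit looks that arrive in sequence, and the section does not fix when a look counts as a flag. Under the assumptions above, (A) raises flags on a single early event and withdraws about three-quarters of its false ones; (B) leaves most of the 5% error unused. Both detect a true 15.9% rate less often (68–72% and 64–67%) than the example boundary (81–82% at 3.8–4.6% false alarms).

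Part of that difference is error spent rather than efficiency. Against (B) it is all unused error; against (A) at equal false alarms with a constant level it is 11–13 points. The practical benefit is mainly a clear, lasting flag: the example rule has fewer false alarms during accrual than (A) (1.9–2.6% against 3.6–4.2%) at broadly similar detection. Section 11.5 is the only statistical interim check on IBTR, but not the only oversight. This should be corrected, but it does not threaten the final analysis.

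**What to change.** Replace the Hochberg sentence with a one-sided boundary fixed before the first look, stated as cumulative IBTRs against accrued person-years at the 5% reference. For example, flag on:

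| IBTRs | Up to person-years |
|---|---|
| 2 | 20 |
| 3 | 55 |
| 4 | 99 |
| 5 | 149 |
| 6 | 203 |
| 7 | 261 |
| 8 | thereafter |

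The cut-offs do not depend on accrual speed or number of looks, although the false-alarm and detection rates do. Another pre-set boundary shape would also serve.

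The section should also:

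- name the test, alpha and sidedness;
- say that a flag stands once raised, and what it leads to;
- report the boundary's false-alarm and detection rates, including the low power at a true 10% rate;
- state that the flag (excess over 5%) is separate from the 3-of-50 rule in 11.4, and report the count against both. At a true 15.9% rate, 16–17% of trials still reach four IBTRs without a flag under the example rule (27–30% under A).

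The cost is revised wording and a short simulation to confirm the level. No extra patients, visits or data are needed.

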11.6 Accrual

It is estimated that less than 10% of the patients treated in this study will be lost to follow up. Therefore, because the accrual goal is 50 evaluable patients (at 5 years post-treatment), target accrual is 55 patients to account for the 10% anticipated drop-out. It is estimated that patient accrual will take two to three years.

The investigators are well aware that several prior clinical trials that involved breast cancer at the Washington University Medical Center and the Siteman Cancer Center suffered from poor accrual. We believe that this trial will have excellent patient accrual. The primary source of patients who may be eligible for this study is via the breast surgeons of the Section of Endocrine and Oncologic Surgery here at Washington University. The chief breast surgeon is a collaborator in this study and is very supportive. The fact that a large fraction of patients with a common cancer disease are eligible for this study should lend further reassurance that this study ought to enjoy excellent patient accrual. The following series of conservative estimates provide an approximation of patient accrual: in 2012 more than four hundred patients with breast cancer were seen by physicians in the Department of Radiation Oncology. A conservative estimate is that 20% of these patients had an early stage breast cancer that would be eligible for this study. A further conservative estimate is that a third of these patients will consent to participate in this study. This yields an estimated accrual of just over 25 patients per year.

APPENDIX I: Patient Evaluation of the Treated Breast

You have been treated with breast-conserving therapy for breast cancer. As you know, a reason for choosing this treatment is the potential for keeping a breast that looks and feels as close to normal as possible. Your opinion concerning the appearance of your breast is valuable to us.

I. Please circle the word below which best describes your judgment of the cosmetic results of therapy at this time:

EXCELLENT	when compared to the untreated breast, there is minimal or no difference in the size or shape of the treated breast. The way the breast feels (its texture) is the same or slightly different. There may be mild thickening or scar tissue within the breast or skin, but not enough to change the appearance.
GOOD	there is mild asymmetry between the breasts, which means that there is a slight difference in the size or shape of the treated breast as compared to the opposite breast. There may be some mild reddening or darkening of the breast. The thickening or scar tissue within the breast causes only a mild change in the shape.
FAIR	moderate deformity of the breast, with an obvious difference in the size and shape of the treated breast. This change involves 1/4 or less of the breast. There is moderate thickening or scar tissue of the skin and the breast, and obvious color changes.
POOR	marked change in the appearance of the treated breast involving more than 1/4 of the breast tissue. The skin changes are very obvious. There is severe scarring and thickening of the breast.

II. In summary, regarding your breast conservation therapy, your overall feeling is:

- A)** completely satisfied with the treatment and results.
- B)** not totally satisfied, but would choose breast conservation therapy again.
- C)** dissatisfied with breast conservation therapy.

III. If you had it all over to do again, would you prefer to have your breast cancer treated:

- A)** just the way you were treated.
- B)** with a mastectomy, not requiring radiation therapy.

IV. It is sometimes very difficult to tell if the changes in your treated breast are due to the surgery, the radiation therapy, or both. Try to remember what the breast looked like after the surgery, but before the radiation treatments began. Now compare that memory to the appearance of the breast now. The changes within your breast at this time are in your opinion:

- A)** caused mostly by the radiation.
- B)** caused by both the radiation and surgery, but mostly by the radiation.
- C)** caused by both the radiation and surgery, but mostly by the surgery.
- D)** caused mostly by the surgery.
- E)** can't judge which treatment caused the change.
- F)** there are no changes.

PLEASE PRINT YOUR NAME: _____ DATE: _____

APPENDIX II: Physician Evaluation of the Treated Breast

The physician should never share his evaluation with the patient, as it may influence subsequent patient evaluations. Also, do not glance at previous evaluations...it is the evolution of cosmetic changes we are studying.

PATIENT'S NAME: _____ DATE: _____
EVALUATOR: _____

I. Please assess the cosmetic results of breast conservation therapy at this time (Circle one):

EXCELLENT when compared to the untreated breast, there is minimal or no difference in the size or shape of the treated breast. The way the breast feels (its texture) is the same or slightly different. There may be mild thickening or scar tissue within the breast or skin, but not enough to change the appearance.

GOOD there is mild asymmetry between the breasts, which means that there is a slight difference in the size or shape of the treated breast as compared to the opposite breast. There may be some mild reddening or darkening of the breast. The thickening or scar tissue within the breast causes only a mild change in the shape.

FAIR moderate deformity of the breast, with an obvious difference in the size and shape of the treated breast. This change involves 1/4 or less of the breast. There is moderate thickening or scar tissue of the skin and the breast, and obvious color changes.

POOR marked change in the appearance of the treated breast involving more than 1/4 of the breast tissue. The skin changes are very obvious. There is severe scarring and thickening of the breast. In retrospect, the breast may have been better treated by a mastectomy.

II. In the physician's opinion, the changes within the treated breast are:

- A)** caused mostly by the radiation.
- B)** caused by both the radiation and surgery, but mostly by the radiation.
- C)** caused by both the radiation and surgery, but mostly by the surgery.
- D)** caused mostly by surgery.
- E)** can't judge which treatment caused the change.
- F)** there are no changes.

III. Instructions: For each of the breast characteristics presented above, please rate the treated breast *as compared to the untreated breast*. Place a check mark in the appropriate cell for each characteristic.

	No Difference	A Small Difference	A Moderate Difference	A Large Difference	Not Evaluable
	0	1	2	3	4
Breast Size					
Breast Shape					
Skin Color					
Location of the areola and nipple					
Shape of the areola and nipple					

IV. How would you rate the appearance of the surgical scars? Please circle your assessment.

- 0 = Very unobtrusive
- 1 = Visible but not affecting cosmetic results
- 2 = Visible and detracting somewhat from cosmetic results
- 3 = Visible and detracting a great deal from cosmetic results
- 4 = Not evaluable

V. Measure and record the Breast Retraction Assessment parameters (see Appendix III):

a₁ = _____

b₁ = _____

a₂ = _____

b₂ = _____

APPENDIX III: Quantitative Cosmetic Analysis

Determining the Breast Retraction Assessment (BRA) and percent BRA (pBRA). From [32]

[figure not shown]

Fig. 1. Illustration of the BRA measurements.

$$\text{BRA} = \sqrt{(a_1 - b_1)^2 + (a_2 - b_2)^2};$$

$$\text{reference length (ref.)} = \sqrt{b_1^2 + b_2^2};$$

$$\text{pBRA} = (\text{BRA}/\text{reference length}) \times 100.$$

APPENDIX IV: EORTC QLQ-C30 and BR23

EORTC QLQ-C30 (version 3)

We are interested in some things about you and your health. Please answer all of the questions yourself by circling the number that best applies to you. There are no "right" or "wrong" answers. The information that you provide will remain strictly confidential.

Please fill in your initials:

Your birthdate (Day, Month, Year):

Today's date (Day, Month, Year):

31

		Not at All	A Little	Quite a Bit	Very Much
1.	Do you have any trouble doing strenuous activities, like carrying a heavy shopping bag or a suitcase?	1	2	3	4
2.	Do you have any trouble taking a long walk?	1	2	3	4
3.	Do you have any trouble taking a short walk outside of the house?	1	2	3	4
4.	Do you need to stay in bed or a chair during the day?	1	2	3	4
5.	Do you need help with eating, dressing, washing yourself or using the toilet?	1	2	3	4

During the past week:

		Not at All	A Little	Quite a Bit	Very Much
6.	Were you limited in doing either your work or other daily activities?	1	2	3	4
7.	Were you limited in pursuing your hobbies or other leisure time activities?	1	2	3	4
8.	Were you short of breath?	1	2	3	4
9.	Have you had pain?	1	2	3	4
10.	Did you need to rest?	1	2	3	4
11.	Have you had trouble sleeping?	1	2	3	4
12.	Have you felt weak?	1	2	3	4
13.	Have you lacked appetite?	1	2	3	4
14.	Have you felt nauseated?	1	2	3	4
15.	Have you vomited?	1	2	3	4

During the past week:		Not at All	A Little	Quite a Bit	Very Much
16.	Have you been constipated?	1	2	3	4
17.	Have you had diarrhea?	1	2	3	4
18.	Were you tired?	1	2	3	4
19.	Did pain interfere with your daily activities?	1	2	3	4
20.	Have you had difficulty in concentrating on things, like reading a newspaper or watching television?	1	2	3	4
21.	Did you feel tense?	1	2	3	4
22.	Did you worry?	1	2	3	4
23.	Did you feel irritable?	1	2	3	4
24.	Did you feel depressed?	1	2	3	4
25.	Have you had difficulty remembering things?	1	2	3	4
26.	Has your physical condition or medical treatment interfered with your family life?	1	2	3	4
27.	Has your physical condition or medical treatment interfered with your social activities?	1	2	3	4
28.	Has your physical condition or medical treatment caused you financial difficulties?	1	2	3	4

For the following questions please circle the number between 1 and 7 that best applies to you

29. How would you rate your overall health during the past week?

1 2 3 4 5 6 7

30. How would you rate your overall quality of life during the past week?

1 2 3 4 5 6 7

EORTC QLQ - BR23

Patients sometimes report that they have the following symptoms or problems. Please indicate the extent to which you have experienced these symptoms or problems during the past week.

During the past week:	Not at All	A Little	Quite a Bit	Very Much
31. Did you have a dry mouth?	1	2	3	4
32. Did food and drink taste different than usual?	1	2	3	4
33. Were your eyes painful, irritated or watery?	1	2	3	4
34. Have you lost any hair?	1	2	3	4
35. Answer this question only if you had any hair loss: Were you upset by the loss of your hair?	1	2	3	4
36. Did you feel ill or unwell?	1	2	3	4
37. Did you have hot flushes?	1	2	3	4
38. Did you have headaches?	1	2	3	4
39. Have you felt physically less attractive as a result of your disease or treatment?	1	2	3	4
40. Have you been feeling less feminine as a result of your disease or treatment?	1	2	3	4
41. Did you find it difficult to look at yourself naked?	1	2	3	4
42. Have you been dissatisfied with your body?	1	2	3	4
43. Were you worried about your health in the future?	1	2	3	4
During the past four weeks:	Not at All	A Little	Quite a Bit	Very Much
44. To what extent were you interested in sex?	1	2	3	4
45. To what extent were you sexually active? (with or without intercourse)	1	2	3	4
46. Answer this question only if you have been sexually active: To what extent was sex enjoyable for you?	1	2	3	4

Please go on to the next page

During the past week:

	Not at All	A Little	Quite a Bit	Very Much
47. Did you have any pain in your arm or shoulder?	1	2	3	4
48. Did you have a swollen arm or hand?	1	2	3	4
49. Was it difficult to raise your arm or to move it sideways?	1	2	3	4
50. Have you had any pain in the area of your affected breast?	1	2	3	4
51. Was the area of your affected breast swollen?	1	2	3	4
52. Was the area of your affected breast oversensitive?	1	2	3	4
53. Have you had skin problems on or in the area of your affected breast (e.g., itchy, dry, flaky)?	1	2	3	4

